2.4 Seminal studies - WHIMS, WHISCA, KEEPS and ELITE

Two Women's Health Initiative (WHI) ancillary studies, the WHI Memory Study (WHIMS) and WHI Study of Cognitive Aging (WHISCA) found that both opposed and unopposed oCEE were associated with adverse cognitive effects. 16,42-45 and no mood benefits 44,45 when initiated in women age 65 or older. Both treatment conditions were associated with greater brain atrophy than placebo.46 To clarify the importance of the age at which mHT was initiated, i.e., proximity to menopause. WHI scientists examined the cognitive function of women enrolled in the WHI trial between the ages of 50 and 55 and found no evidence of cognitive benefit or harm more than a decade after mHT was initiated.⁴⁷ The KEEPS and its ancillary KEEPS-Cog, and the Early vs. Late Intervention with Estradiol (ELITE) trials were launched in order to address remaining controversies. In KEEPS, mHT was initiated close to the age of menopause; whereas ELITE compared women randomized to mHT within six years of menopause to women exposed more than 10 years past menopause. 32 A review of KEEPS and KEEPS-Cog is provided in our Preliminary Studies. Cardiovascular findings from ELITE suggested that early but not late intervention slowed atherosclerosis. 33 Interestingly, the ELITE cognitive trial found no difference in the cognitive effects of mHT based on timing of exposure. 48 Neither KEEPS-Cog nor ELITE has reported on *long-term effects* of mHT's. In contrast to WHIMS findings, data from the Prospective Epidemiological Risk Factors (PERF) study suggest that younger women (mean age 54.1) randomized to mHT performed better on cognitive outcomes than women treated with placebo, 5 to 15 years after study involvement ended. 49 It should be noted that in addition to differences in timing of mHT, the formulations of hormones differed among studies. In the WHI, the formulations were oCEE with medroxyprogesterone acetate, a synthetic progestogen. 50 In the ELITE trial, oral 17β-estradiol plus micronized progesterone was used.³² In the KEEPS, two formulations were compared to placebo: oCEE at a lower dose than in the WHI was used (0.45mg/day) and transdermal 17β-estradiol; each paired with a pulsed micronized progesterone. The formulations used in KEEPS are those most commonly used in clinical practice today. Thus, the KEEPS Continuation study will address inconsistencies in findings, clarifying the effects of mHT on AD biomarkers and cerebrovascular contributions and provide the needed information regarding the long -term cognitive effects of mHT treatments used in current clinical practice.

2.5 Understanding the mechanisms of mHT effects on the brain through imaging biomarkers

F-18 Florbetapir PET directly measures the β-amyloid (Aβ) pathology of AD.⁵¹ A positive Aβ PET scan is proposed as a research criterion for preclinical AD.^{52,53} Carriers of the *APOE* ε4 allele are at an increased risk of AD dementia; moreover the risk may be higher in women than in men. ⁵⁴⁻⁵⁶ *APOE* ε4 carriers have increased Aβ deposition at an earlier age than *APOE* ε4 non-carriers,

and this difference is more pronounced in women than in men. ^{57,58} Thus, women who are APOE ε4 carriers are at a higher risk for AD-related Aβ deposition and may benefit most from early initiation of preventive interventions. The age of KEEPS participants we plan to recruit for the current project will be between ages 54 to 70 (median age=65). In the population-based Mayo Clinic Study of Aging (MCSA), 18% of the women have a positive A\(\beta\) PET scan at this age range. Aβ PET scan positivity is approximately three times higher in women who are APOE ε4 carriers (33% positive) compared to APOE ε4 non-carriers (11% positive) in this age range. Similarly, in the Longitudinal Baltimore Study of Aging, APOE £4 positivity conferred a threefold risk of accumulating Aβ after adjusting for sex and education.⁵⁹ Although estrogens are thought to modify AD risk, there are only limited data on the estrogen effects on Aβ.60 Effects of mHT on brain morphology have been investigated in cross-sectional observational MRI studies, with varying findings in cognitively normal postmenopausal estrogen users compared to nonusers. 21,61-66 As for all observational studies, these imaging studies are subject to "healthy user bias". Contrary to the findings from observational studies, data from WHIMS indicate greater hippocampal atrophy in postmenopausal women who are treated with oCEE at age 65 years and older. 46 In WHIMS, women with low baseline cognitive function and high ischemic WMH burden were more prone to this treatment effect on the hippocampus, suggesting greater vulnerability to mHT-associated atrophy for already compromised brains. 46,67 Furthermore, hippocampal volumes correlated with cognitive function in the treated group, suggesting oCEE induces cognitive impairment through increased brain atrophy.⁶⁸ WMHs were associated with baseline blood pressure in WHIMS, and a greater longitudinal increase in WMH occurred in those with higher blood pressure demonstrating the longitudinal blood pressure effects on the ischemic WMH.⁶⁹ MRI findings in WHIMS are consistent with the previously reported decline in cognitive function and increased risk of dementia with oCEE in this cohort, and demonstrate that MRI-based measures of brain morphology are robust biomarkers of cognitive function in postmenopausal women. Additionally, there is evidence that WMH load is associated with small vessel disease in the brain. 67,70 Hypertensive renal disease is strongly associated with WMH,71 and a better control of blood pressure slows WMH progression.^{72,73} An association between WMH load and future risk for mild cognitive impairment is established. 74-76 The KEEPS Continuation Study will examine these underlying disease-associated changes, relating to long term cognitive effects of two formulations of mHT.

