- interventions and Buration
 - Explanation of the study and confirmation of eligibility
 - Measurement of height, weight, waist and hip circumference, blood pressure
 - and pulse
 - Review of medical history
 - o Blood tests
 - Questionnaires about general health and well-being, COVID-19 questionnaire quality of life, sleep, emotional health and mood and pregnancy history.
 - Neurocognitive tests
 - Brain magnetic resonance imaging (MRI)
 - Brain positron emission tomography (PET): F-18 Florbetapir PET (all sites) and F-18 AV-1451 PET (only at the Mayo Clinic & BAI site)
 - All tests and procedures will take about 9 hours total to complete.

Participants will be on study until all of the following are completed: medical assessment, questionnaires, blood work, neurocognitive studies, , brain MRI, brain PET.

Sample Size and Population

Our targeted enrollment is 492 (n=83 at the Mayo Clinic) participants across eight sites; 13 years post-randomization (4 years of study drug and 9 years after the end of study drugs).

Women who enrolled in the KEEPS study at 8 sites will be invited to participate (total n=688; Mayo Clinic n=118). In order to reduce the costs but retain as many participants as possible, we merged the cohorts in two sites by taking advantage of the proximity of geographic location. Columbia University will be recruiting the Einstein Montefiore Center's participants; therefore 7 sites including Mayo Clinic Rochester will be participating.

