8. STATISTICAL CONSIDERATIONS

9.1 General Design Issues

The proposed analytical plan will comprise 1) data cleaning and basic statistical analyses to identify potential outliers, assess for normality, and examine variation in each variable; 2) the generation of standard descriptive statistics summarizing the sample and its characteristics; and 3) statistical methods for analyzing each specific aim and hypothesis. For each aim, all calculated P values will be 2-sided and P<.05 will be considered statistically significant.

9.2 Primary Objective 1

To determine the differences in A β , cerebrovascular lesion load and brain structure in postmenopausal women who were treated with one of two mHTs vs. placebo after 13 years post-randomization and 9 years after the end of mHT administration phase.

Primary Hypothesis: Aβ PET SUVR (primary outcome), AV-1451 SUVR, WMH volume and regional cortical thickness (or hippocampal volume) are different in women who were treated with tE2 vs. placebo and oCEE vs. placebo.

Hypothesis 1a: Aβ PET SUVR (primary outcome), AV-1451 SUVR, WMH volume and regional cortical thickness (or hippocampal volume) differences in women who were treated with tE2 vs. placebo and oCEE vs. placebo are modified by the *APOE*e4 status (carrier/noncarrier).

Hypothesis 1b: Aβ PET SUVR (primary outcome), AV-1451 SUVR, WMH volume and regional cortical thickness (or hippocampal volume) differences in women who were treated with tE2 vs. placebo and oCEE vs. placebo during early post menopause are modified by the vascular disease risk at 13 years post-randomization.

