Statistical Analysis for Aim 1: We will first summarize the data for Aim 1 using standard descriptive statistics and a variety of plots (histograms, scatterplots) to assess variable distributions. Our outcome measures: Aß PET SUVR (primary outcome), WMH volume, and regional cortical thickness (or hippocampal volume) for this aim will all be continuous crosssectional variables, we will use analysis of covariance (ANCOVA) to address the primary hypothesis. Treatment groups (tE2, oCEE, and placebo) will be included as the predictors of interest, coded so that placebo is the reference group. Standard methods (Least Significant Difference, Tukey's Honest Significant Difference, and Scheffé's test) will be used to assess pairwise differences. We will include a set of dummy variables to test and adjust for site (block) effects. The outcome variables will be transformed as necessary to meet regression assumptions underlying the ANCOVAs. These analyses will include baseline age, time from baseline, and APOE ε4 status (as appropriate) as covariates. We will test for interactions of treatment with APOE ε4 status through inclusion of two-way interactions in the models, and analyses in separate APOE £4 non-carrier and APOE £4 carrier strata. To address Hypothesis 1a, we will expand the set of covariates to include a vascular disease risk score assessed at the time of mHT/placebo initiation(82) or individual cardiovascular risk factors (systolic and diastolic BP, fasting glucose, smoking history, lipid profile, BMI, waist circumference). Possible interactions with these covariates will be handled in the same way as APOE ε4 status. Hypothesis 1b will be treated much the same way, but CVD risk scores will be constructed from data acquired at 13 years after initiation of mHT. Since some of the women in the study might have used mHT after the trial ended, we will perform a series of sensitivity analyses with and without those individuals to assess any important effects and ensure that the final conclusions are robust.

Power for Aim 1: Focusing on Florbetapir PET, our primary outcome variable for Aim 1, we first estimated the standard deviations in three groups of women (all subjects, APOE ε4 non-carriers, and APOE ε4 carriers) from the Mayo Clinic Study of Aging, a longitudinal study on aging and dementia. We identified women with an age range of 55-70 (mean age=65) similar to our projected sample, who underwent both Aβ PET imaging and APOE ε4 testing (n=264) Using

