
these standard deviations as estimates of variability in our projected sample, we estimated the minimum detectable effect sizes in the pairwise comparisons (using Cohen's d) with 80% power.

Table 3. Minimum detectable effect sizes for projected sample size and 80% power.

Comparison	All	APOE ε4 non-carriers	APOE ε4 carriers
oCEE vs. Placebo	0.308	0.358	0.619
tE2 vs. Placebo	0.312	0.355	0.665

These effect sizes fall in the medium (all and $APOE\ \epsilon 4$ non-carriers) to large ($APOE\ \epsilon 4$ carriers) range. In our 84 month KEEPS data, most of our observed Cohen's d values were close to 0.34 (all subjects), 0.37 ($APOE\ \epsilon 4$ non-carriers), and 1.18 ($APOE\ \epsilon 4$ carriers). We anticipate the effect sizes to be at least this large in the KEEPS Continuation study. Since the minimum detectable effect sizes in **Table 3** are close to or smaller than these values, we anticipate having adequate power to detect pairwise differences. We would expect similar effect sizes for the other outcomes.

9.3 Primary Objective 2

To determine the differences in longitudinal changes in cognitive performance and mood in postmenopausal women who were treated with one of the two mHTs vs. placebo.

Primary Hypothesis 2: Performance on four cognitive factors described in our bi-factor model and on POMS mood indices are different in women who were treated with tE2 vs. placebo and oCEE vs. placebo.

Hypothesis 2a: Cognitive and mood differences in women who were treated with tE2 vs. placebo and oCEE vs. placebo are modified by *APOE*e4 status (carrier/noncarrier).

Hypothesis 2b: Cognitive and mood differences in women who were treated with tE2 vs. placebo and oCEE vs. placebo are modified by the vascular disease risk at 13 years post-randomization.

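### The main WMH comparison omits a pre-randomisation vascular covariate that the plan already has; prespecifying one would be a small, nearly free gain in precision

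*Combined protocol and SAP*

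**What the plan says.** The background in section 2.5 reports from WHIMS that "WMHs were associated with baseline blood pressure in WHIMS, and a greater longitudinal increase in WMH occurred in those with higher blood pressure". It adds that better blood pressure control slows WMH progression.

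Section 9.2 lists WMH volume among the Aim 1 outcomes and labels Aβ PET SUVR as primary. One ANCOVA is given for all of these outcomes, with treatment arm, site dummies and a common covariate list: "These analyses will include baseline age, time from baseline, and APOE ε4 status (as appropriate) as covariates". Blood pressure is not on the list.

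The same section then turns to Hypothesis 1a, for which "we will expand the set of covariates to include a vascular disease risk score assessed at the time of mHT/placebo initiation", or alternatively individual cardiovascular risk factors, among them systolic and diastolic pressure. Interactions with these covariates are dealt with in a separate sentence. Hypothesis 1b uses risk scores built from 13-year data. In the hypotheses at the head of 9.2, however, 1a concerns APOE ε4 status, and only 1b concerns vascular risk.

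**The concern.** Adjusting a randomised comparison for a pre-randomisation predictor of the outcome reduces residual variance and costs about one degree of freedom per covariate. The plan follows this logic for amyloid: section 2.5 argues that APOE ε4 drives Aβ deposition, and APOE ε4 is in the main model. For WMH the same section names blood pressure, yet the main model has no vascular term, although the plan treats vascular risk at treatment start as available.

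WMH volume is the only cerebrovascular measure named in the 9.2 hypotheses. Infarcts are also read (10.4.3), but few are expected.

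Two things are at stake. One is a modest loss of precision in the tE2 and oCEE contrasts with placebo. The other is discretion: both a main and a vascular-adjusted WMH contrast will exist. The second has an unresolved choice of covariates and a hypothesis label that does not match its content. Nothing says which contrast decides if they differ.

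**Working it through.** **Inputs from the documents**
- Significance level (9.1): "For each aim, all calculated P values will be 2-sided and P<.05 will be considered statistically significant".
- Sample size (Précis): "Our targeted enrollment is 492 (n=83 at the Mayo Clinic) participants across eight sites". Arm sizes are not given, so I assume equal arms: 492/3 = 164.
- Table 3 (9.2), all women, 80% power: minimum detectable Cohen's d of 0.308 (oCEE vs placebo) and 0.312 (tE2 vs placebo). These were computed for Florbetapir PET. For WMH the plan only expects similar effect sizes and gives no SD.

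**Input not in the documents**
- R², the share of WMH variance (on the analysis scale) that the baseline vascular covariate explains beyond the covariates already in the model. Assumed range: 0.01 to 0.10.

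**Step 1: reproduce the plan's figure**

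MDE = (1.960 + 0.842) × √(2/164) = 2.8016 × 0.11043 = 0.309.

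This agrees with 0.308 and 0.312. Power at those two values with 164 per arm is 79.6% and 80.7%. The printed values correspond to about 166 and 162 women per arm, consistent with slightly unequal arms.

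**Step 2: add the covariate**

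The residual SD is multiplied by √(1 − R²), so MDE = 0.3094 × √(1 − R²). The 492 women then carry the information of 492/(1 − R²). Power is shown at d = 0.31.

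| Assumed R² | MDE | Power at d = 0.31 | Equivalent total N |
|---|---|---|---|
| 0 (as planned) | 0.309 | 80.2% | 492 |
| 0.01 | 0.308 | 80.5% | 497 |
| 0.02 | 0.306 | 80.9% | 502 |
| 0.05 | 0.302 | 82.1% | 518 |
| 0.10 | 0.294 | 84.1% | 547 |

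**Step 3: what R² would matter**

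A gain of 2 power points needs R² of about 0.05. A gain of 5 points needs about 0.125, which is outside the assumed range.

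**Step 4: compare the text within 9.2**
- The primary-hypothesis model has no vascular term.
- The expanded model has a baseline vascular term, but in one of two alternative forms.
- That model is labelled 1a, yet 1a as stated is about APOE ε4 and 1b is about vascular risk at 13 years. The baseline vascular model therefore matches no stated hypothesis, and its role for WMH is open.

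**The case against.** The strongest reply is that the plan already contains a WMH analysis with baseline vascular adjustment. The expanded model adds these factors as covariates first, and interactions come afterwards. A reader might infer that baseline blood pressure is missing from the plan altogether, and that is not so. What stands is narrower: it is absent from the model for the primary hypothesis, and no model is named as deciding for WMH.

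A second reply concerns the evidence. The blood pressure finding comes from WHIMS, where treatment began at 65 or older. KEEPS women enrolled at 42–58, with no prior cardiovascular events and minimal cardiovascular risk. Their entry blood pressure would have to predict WMH some 13 years later, and no figure is given. This is fair, and it makes the low end of the assumed range quite possible. The statement about blood pressure control concerns continuing control rather than a single baseline value.

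A reader might also infer bias, since only about 70% are expected to return. The documents do not support that. Leaving out a baseline covariate does not by itself bias a randomised contrast, and chance imbalance is already reflected in the standard error. Return is not randomised, but nothing in the documents indicates that it differs by arm according to blood pressure.

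Finally, the documents do not favour systolic pressure alone over diastolic pressure or the baseline score they already name.

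**Conclusion.** The point holds as a low-cost improvement in precision and clarity for a non-primary Aim 1 outcome. The main WMH contrasts carry some noise that an available baseline covariate could remove, and the deciding WMH model is not fixed.

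With equal arms of 164 and an assumed R² of 1–10%, the minimum detectable effect moves from 0.309 to between 0.308 and 0.294. Power at d = 0.31 rises from 80.2% to between 80.5% and 84.1%. The gain stays under 2 points unless R² exceeds about 0.05, and the documents do not show where in the range it lies.

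It would go too far to conclude that the WMH comparison is invalid, biased or badly underpowered. It would also be wrong to read this as affecting the primary outcome, Aβ PET SUVR.

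**What to change.** In section 9.2, for the WMH outcome and before unblinded analysis:

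1. Add one KEEPS-baseline vascular covariate to the main ANCOVA, either baseline blood pressure or the baseline vascular risk score. State which, and how it is coded, so that the choice between score and individual factors is closed for this model.
2. Name that model as the deciding WMH analysis.
3. Keep the interaction analyses as a separate step, and correct the label so that the baseline vascular model is tied to a stated hypothesis.
4. State that year-13 vascular values are not used for this adjustment, because they are measured after treatment.

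The cost is a change of wording in the analysis plan and about one degree of freedom. The plan already treats the data as available, so no new collection should be needed.

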
2.6 Overall Impact

Findings from the KEEPS Continuation Study hold the potential to alter the clinical practice paradigms related to treatment of menopausal symptoms and prevention of AD. For the more than 4.5 million postmenopausal women in the world and the women currently using mHT, clarifying the long-term effects of different types and formulations of mHT on the brain is critical.

The KEEPS Continuation study will be unique in clarifying inconsistencies in the literature regarding mHT and cognitive health in the following ways: 1) Provide information regarding potential preventive or risk effects of clinically relevant formulations of mHT on AD biomarkers and cerebrovascular lesions; 2) Provide 13 year follow-up of cognitive change in women who initiated mHT early in menopause; 3) Evaluate the efficacy of mHT relative to APOE ε4.

3. STUDY DESIGN

This is a continuation of the Kronos Early Estrogen Prevention Study (KEEPS) (KEEPS; NCT00154180; Mayo Clinic IRB #2241-04-00), a multicenter double blinded, placebo-controlled, randomized trial (NCT00154180) funded by the Kronos Longevity Research Institute, Phoenix, AZ to test the hypothesis that hormone therapy started early in menopause (within the **"window of opportunity"**) would slow progression of atherosclerosis as measured by changes in carotid artery intima-medial thickening and coronary arterial calcification. Enrollment in the KEEPS ended in 2008 with the final study visits occurring in late 2012.⁷⁸ 727 healthy menopausal women aged 42 to 58 years, all within 36 months from last menses without prior CVD events were enrolled at nine US

academic sites.

4. SELECTION AND ENROLLMENT OF PARTICIPANTS

This proposal is developed as a continuation of the Kronos Early Estrogen Prevention Study (KEEPS; NCT00154180; Mayo Clinic IRB #2241-04-00).

This study will involve a single follow-up evaluation of brain imaging and cognitive function of all women who were randomized to mHT or placebo, approximately 13 years post-randomization and nine years after the end of mHT administration phase in KEEPS. All women who were enrolled in KEEPS in the eight sites will be invited to participate. Names and contact information of the participants were retained by site PIs.

Table 1. Study timeline and enrollment plan and assuming 70% participation rate

Site	Year 1		Year 2	Year 3	Year 4	Year 5	Total
Brigham & Women's	Preparation phase		21	21	15	Analysis	57
Columbia & Einstein	Preparation		42	42	30	Analysis	142
Mayo Clinic	Preparation phase		30	30	22	Analysis	83
University of San Francisco	Preparation phase		6	19	14	Analysis	39
University of Utah	Preparation phase		24	24	16	Analysis	64
Banner Alzheimer's Institute	Preparation phase		7	23	16	Analysis	46
Yale University Preparation 1		10	20	20	11	Analysis	51
Total		38	150	179	125		492

Each woman will be invited to participate by a letter from the study coordinator at each site. For those women expressing interest, the study coordinator will provide a detailed description of the study and those who are willing to participate will be scheduled for study visits at 13-year post-randomization landmark. Information on current use of medications and interim cardiovascular, cerebrovascular, or neurologic disease events will be collected during the clinical visit. Study participants will be scheduled to complete all assessments and tests over three or four visits. Study data will be de-identified and transferred to the Mayo Clinic and UW through secure file transfer protocols. Data will be stored at each institution's data center.

For participants that have moved away from the site in which they originally were enrolled, may participate at one of the participating sites listed that is closest to their new address. Once they have responded that they are willing to participate at a different site, contact information will be given to the new enrolling site in order to communicate with the participant for Consenting, Enrollment and Scheduling Visits.

At Mayo Clinic, 118 women met the inclusion criteria for randomization into the KEEPS trial. This study will recruit these 118 menopausal women for follow-up. Assuming a 70% retention rate, we project that our cohort will consist of approximately 82 subjects.

